11.6.2 Safety Data

Summaries and analysis of safety data will be presented for the Safety Analysis Population. All summaries and analyses will be presented for all subjects, and by age stratum.

Solicited AEs will be summarized by severity for each day after each study vaccination (Days 1-7 post each study vaccination) and as the maximum severity over all 8 days. Additionally, solicited AEs will be analyzed by taking the most severe response over the follow-up period, dichotomizing into a binary variable (none versus mild, moderate, or severe) and using standard techniques, such as exact confidence intervals, to summarize the proportion of subjects reporting each symptom, any injection site symptom, and any systemic symptom. Summaries of solicited AEs will be presented separately for each study vaccination as well as overall study vaccinations by treatment arm. The proportion of subjects reporting symptoms may be compared between

treatment arms using Chi-square or Fisher's exact test. The proportion of subjects reporting solicited symptoms between the different study vaccinations (i.e., first and second) will be compared using McNemar's test.

Unsolicited AEs will be coded by Medical Dictionary for Regulatory Activities (MedDRA®) for preferred term and system organ class (SOC). The numbers of SAEs, MAAEs, including NOCMCs, and PIMMCs are likely to be small in this trial and will be reported by detailed listings showing the event description, MedDRA® preferred term and SOC, relevant dates (study vaccinations and AEs), severity, relatedness, and outcome for each event. Non-serious unsolicited AEs will be summarized as number and percentage of subjects reporting at least one event in each MedDRA® preferred term and SOC, cross tabulated by severity and relationship to study product. Additionally, the proportion of subjects and exact 95% confidence intervals of AEs in aggregate and by MedDRA® categories will be computed.

Clinical laboratory data will be summarized by severity for each visit and as the maximum over all post-study vaccination visits. Graphical presentations may include box plots.

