- @ Complete medical history will be obtained by interview of subjects at the first visit (either screening [optional] or on Day 1 prior to the first study vaccination) and interim medical history will be obtained by interview of subjects at subsequent visits.
- 6 Receipt of non-study influenza vaccines will be solicited through approximately 180 days after the last study vaccination, and reported in the eCRF.
- [%] Subjects must not eat or drink anything hot or cold, or smoke within 10 minutes prior to taking oral temperature.
- {} Targeted physical examination if indicated based on review of interim medical history.
- ~ Includes WBC, Hgb, PLT, ALT, T. Bili, Cr
- Ψ Subjects who do not receive the second study vaccination will continue with follow-up safety assessments (may be conducted by phone call) rather than in person continuing through approximately 12 months after their first study vaccination. These subjects will also be encouraged to provide a venous blood sample for immunogenicity assays at approximately 21 and 180 days after their first study vaccination
- For subjects who have consented to collection of serum for future use either by signing an informed consent form that includes collection of future use samples as a condition of study participation or by indicating that they opt in to sample collection for future use if the informed consent form allows the option to choose that option.
- [#] AEs will be limited to SAEs and MAAEs, including NOCMCs and PIMMCs if after 21 days after last study vaccination

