3.2.2. Secondary

Safety:

- Occurrence of study vaccine-related unsolicited non-serious AEs from the time of each study vaccination through approximately 21 days after each study vaccination.
- Occurrence of all unsolicited adverse events, regardless of the assessment of seriousness or relatedness, from the time of each study vaccination through approximately 21 days after each study vaccination.
- Occurrence of MAAEs, including NOCMCs, and PIMMCs from the time of the first study vaccination through approximately 12 months after the last study vaccination.
- Occurrence of all serious adverse events (SAEs), regardless of the assessment of relatedness, from the time of the first vaccination through approximately 12 months after the last study vaccination.

Immunogenicity:

- For HAI and Neut antibodies, percentage of subjects achieving seroconversion against the influenza 2017 H7N9 vaccine strain at approximately 7, 21, and 28 days after the first study vaccination (Study Days 8, 22, 29).
- For HAI and Neut antibodies, percentage of subjects achieving titers of 1:40 or greater against the influenza 2017 H7N9 vaccine strain at baseline and approximately 7, 21, and 28 days after the first study vaccination (Study Days 8, 22, 29).
- GMTs of serum HAI and Neut antibodies against the influenza 2017 H7N9 vaccine virus at baseline and approximately 7, 21, and 28 days after the first study vaccination (Study Days 8, 22, 29).

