9.3.2. Unsolicited Adverse Events

When calculating the incidence of unsolicited AEs (i.e., on a per subject basis), each subject will only be counted once at the highest severity and/or relationship, and any repetitions of AEs within a subject will be ignored; the denominator will be the total number of subjects in the safety population. All AEs reported will be included in the summaries and analyses.

The number and percentage of subjects reporting at least one unsolicited AE will be summarized by MedDRA system organ class and preferred term. A 95% CI will be presented for the percentage of subjects reporting any unsolicited AE (serious or non-serious) for each MedDRA system organ class and preferred term over all study vaccinations (Table 94 and Table 95).

The following summaries for unsolicited AEs will be presented by MedDRA system organ class, preferred term, and treatment arm:

- Incidence of AEs by severity and relationship to study product (Table 96);
- Incidence of non-serious, related AEs by severity (Table 97);
- Incidence of AEs over time (Days 1-8, Days 9-22 post each study vaccination) (Table 98);
- Incidence of non-serious, related AEs over time (Days 1-8, Days 9-22 post each study vaccination) (Table 99) note this table presents results for secondary safety endpoint, "Occurrence of study vaccine-related unsolicited non-serious AEs from the time of each study vaccination through approximately 21 days after each study vaccination";
- Total frequency of AEs over time (Days 1-8, Days 9-22 post each study vaccination) (Table 100);
- Subject listing of non-serious AEs of moderate or greater severity (Table 104);
- Bar chart displaying total frequency of AEs by severity and MedDRA system organ class, Treatment Arm, and Age Stratum (Figure 21);

- Bar chart displaying incidence of AEs by severity and MedDRA system organ class, Treatment Arm, and Age Stratum (Figure 22);
- Bar chart displaying total frequency and incidence of AEs by relationship to study product and MedDRA system organ class, Treatment Arm and Age Stratum (Figure 23 and Figure 24).

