14.3.1.2 Unsolicited Adverse Events

Table 94: Number and Percentage of Subjects Experiencing Unsolicited Adverse Events with 95% Confidence Intervals by MedDRA System Organ Class and Preferred Term, and Treatment Arm – Safety Population *

		3.75 A/H + A	oup 1 5 mcg 17N9 AS03 =X)	Group 2 7.5 mcg A/H7N9 + AS03 (N=X)		7.5 mcg A/H7N9 + AS03		Group 3 15 mcg A/H7N9 + AS03 (N=X)		15 mcg A/H7N9 + AS03		Group 4 15 mcg A/H7N9 (N=X)		Group 5 45 mcg A/H7N (N=X)	
MedDRA System Organ Class	MedDRA Preferred Term	n	% (95% CI)	n	% (95% CI)	n	% (95% CI)	n	% (95% CI)	n	% (95% CI)				
Any SOC	Any PT	X	xx (xx-xx)	Х	xx (xx-xx)	х	xx (xx-xx)	х	xx (xx-xx)	х	xx (xx-xx)				
[SOC 1]	Any PT														
	[PT 1]														
	[PT 2]														
[SOC 2]	Any PT														
	[PT 1]														
	[PT 2]			. 1	·	. 1.1	. 1			1: .:	1 . 1				

Note: N = number of subjects in the Safety Analysis Population who received any study vaccination. This table presents number and percentage of subjects. A subject is only counted once per PT.

Table 95: Number and Percentage of Subjects Experiencing Unsolicited Adverse Events with 95% Confidence Intervals by MedDRA System Organ Class and Preferred Term, Treatment Arm and Age Stratum – Safety Population *

MedDRA System Organ Class	MedDRA Preferred Term		Group 1 3.75 mcg A/H7N9 + AS03 (N=X)			Group 2 7.5 mcg A/H7N9 + AS03 (N=X)			Group 3 15 mcg A/H7N9 + AS03 (N=X)			N9		15 mcg	roup 4 g A/H7N9 N=X)			Gro 45 mcg . (N=	A/H7N	N9	
		1	9-64	2	≥ 65	1:	9-64	2	≥ 65	1	9-64	2	≥ 65	1	9-64	2	≥ 65	1	9-64	2	≥ 65
		n	% (95% CI)	n	% (95% CI)	n	% (95% CI)	n	% (95% CI)	n	% (95% CI)	n	% (95% CI)	n	% (95% CI)	n	% (95% CI)	n	% (95% CI)	n	% (95% CI)
Any SOC	Any PT	Х	xx (xx- xx)	Х	xx (xx- xx)	Х	xx (xx- xx)	Х	xx (xx- xx)	X	xx (xx- xx)	Х	xx (xx- xx)	х	xx (xx- xx)	Х	xx (xx- xx)	Х	xx (xx- xx)	Х	xx (xx- xx)
[SOC 1]	Any PT																				
	[PT 1]																				
	[PT 2]																				
[SOC 2]	Any PT																				
	[PT 1]																				
	[PT 2]																				

Note: N = number of subjects in the Safety Analysis Population who received any study vaccination. This table presents number and percentage of subjects. A subject is only counted once per PT.

Table 96: Number and Percentage of Subjects Experiencing Unsolicited Adverse Events by MedDRA System Organ Class and Preferred Term, Maximum Severity, Relationship, Treatment Arm and Age Stratum – Safety Population*

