14.3.1.2 Unsolicited Adverse Events

Figure 21: Frequency of Unsolicited Adverse Events by MedDRA System Organ Class and Severity

[Implementation Note: A Generic figure is shown below. This figure includes all unsolicited events across all vaccinations. A *horizontal* bar chart should be presented *in 3 image files (overall and by strata)* with separate panels for each treatment arm (5 columns (treatment arms)). Axes should be labeled as follows: y-axis label: System Organ Class, y-axis label: Number of Events. The treatment arms should be indicated in the panel headers including "(N=X)", where N = the number of subjects in the in the Safety Population. The y-axis should present all SOCs reported by at least 1 subject and an "All Events" category. Y-axis should be sorted with "All Events first, then in decreasing order of total incidence]

[figure not shown]

Figure 22: Incidence of Unsolicited Adverse Events by MedDRA System Organ Class and Severity

[Implementation Note: A Generic figure is shown below. This figure includes all unsolicited events across all vaccinations. A *horizontal* bar chart should be presented *in 3 image files* with separate panels for each treatment arm (5 columns). Axes should be labeled as follows: y-axis label: System Organ Class, x-axis label: Percentage of Subjects (%). The treatment arms should be indicated in the panel headers including "(N=X)", where N = the number of subjects in the in the Safety Population. Subjects are counted at most once at the maximum severity across for any events in the applicable SOC. The y-axis should present all SOCs reported by at least 1 subject and an "All Events" category. Y-axis should be sorted with "All Events" first then in decreasing order of total incidence]

[figure not shown]

Figure 23: Frequency of Adverse Events by MedDRA System Organ Class and Relationship to Treatment

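### The unsolicited-AE tables with confidence intervals, severity and relatedness (SAP Tables 94-96) have no onset window, so the 21-day endpoints get counts and percentages but no exact 95% CI

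*SAP*

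**What the plan says.** **Endpoints.** SAP 3.2.2 and Protocol 3.2.2 define two unsolicited-AE endpoints: related non-serious AEs, and "Occurrence of all unsolicited adverse events, regardless of the assessment of seriousness or relatedness". Both run from each vaccination through about 21 days after it. MAAEs (with NOCMCs), PIMMCs and SAEs are separate endpoints running to about 12 months after the last dose.

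**Collection.** Protocol Appendix A states for the follow-up period: "AEs will be limited to SAEs and MAAEs, including NOCMCs and PIMMCs if after 21 days after last study vaccination". The last contact is Day 387.

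**Inclusion rule.** SAP 9.3.2 says "All AEs reported will be included in the summaries and analyses". It gives a window (Days 1-8 and 9-22 after each vaccination) only for Tables 98, 99 and 100.

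**Shells.**
- Table 94 is titled "Number and Percentage of Subjects Experiencing Unsolicited Adverse Events with 95% Confidence Intervals by MedDRA System Organ Class and Preferred Term, and Treatment Arm". Neither it nor Table 95, its age-stratum version, names a window in title, columns or footnote.
- Table 96, "Unsolicited Adverse Events by MedDRA System Organ Class and Preferred Term, Maximum Severity, Relationship, Treatment Arm and Age Stratum", names none either.
- Table 97 (related non-serious AEs by severity) names none.
- The implementation notes for Figures 21-24 say "This figure includes all unsolicited events across all vaccinations".
- Tables 98 and 99 are limited by title to 21 days and have a Day 1-22 Post Any Vaccination column, with n and % only.

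**Protocol plan.** Protocol 11.6.2 tabulates non-serious unsolicited AEs by severity and relationship, and adds exact 95% CIs for AEs in aggregate and by MedDRA category. Of the longer-term events it says "The numbers of SAEs, MAAEs, including NOCMCs, and PIMMCs are likely to be small in this trial and will be reported by detailed listings".

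**The concern.** A proportion with a confidence interval should estimate a defined quantity. Read as written, Tables 94-96 count a subject who had any AE in the weeks after a dose, or who had a medically attended or serious event at any later time up to a year. That is neither the 21-day endpoint nor the 12-month MAAE endpoint.

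Late events that do not depend on arm raise the percentage in every arm and shrink the absolute difference between arms. A reader who takes the interval in Table 94 as the precision of the 21-day endpoint would be reading the wrong quantity. The table that does match the endpoint, Table 98, has no interval.

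**Working it through.** **Step 1: do late events enter these tables?** Protocol 9.2.1 identifies MAAEs by asking about medical attention for each unsolicited AE, so an MAAE is an unsolicited AE. Listing 11, the unsolicited-AE listing, carries SAE, MAAE and PIMMC flags. SAP 9.3.2 describes Tables 94-95 as covering serious or non-serious AEs over all study vaccinations. With all reported AEs included and no window, late MAAEs and SAEs count.

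**Step 2: which display gives what?**

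| Display | 21-day window | 95% CI | Severity | Relatedness |
|---|---|---|---|---|
| Tables 94, 95 | no | yes | no | no |
| Table 96 | no | no | yes | yes |
| Table 97 (related non-serious only) | no | no | yes | by selection |
| Table 98 | yes | no | no | no |
| Table 99 (related non-serious only) | yes | no | no | by selection |

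No row has both a window and a CI, or both a window and severity. For all AEs, no row has both a window and relatedness.

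**Step 3: how much follow-up lies outside the window?** With nominal visits, the second 21-day window ends at Day 43 and follow-up ends at Day 387: (387 - 43)/387 = 344/387 = 89%.

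**Step 4: illustration of size.** The plan gives no AE rates, so it has no figure to reproduce on this point. As a check of the interval method, Clopper-Pearson at 80/160 gives 42.0-58.0, which matches SAP Table 5 (42-58).

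Assume a proportion *a* of an arm has an AE within the window. Assume also that a proportion *m* has a later SAE/MAAE-type event, independent of arm and of earlier AEs. The reported proportion is then *a* + (1 - *a*)*m*, and a difference between arms is multiplied by (1 - *m*). With *a* = 20% and 30%:

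| *m* (assumed) | Lower arm | Higher arm | Difference |
|---|---|---|---|
| 0 | 20% | 30% | 10 points |
| 5% | 0.20 + 0.80 × 0.05 = 24% | 0.30 + 0.70 × 0.05 = 33.5% | 9.5 |
| 20% | 0.20 + 0.80 × 0.20 = 36% | 0.30 + 0.70 × 0.20 = 44% | 8 |
| 30% | 0.20 + 0.80 × 0.30 = 44% | 0.30 + 0.70 × 0.30 = 51% | 7 |

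For one adjuvanted arm of 160 with 30% in the window, the exact interval is 23-38% (48/160). The unwindowed table would show 26-42% (54/160) at *m* = 5% and 43-59% (82/160) at *m* = 30%.

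This applies to the row for any SOC and any preferred term. For a single term the late rate, and so the distortion, would be smaller.

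**The case against.** **The 21-day endpoints are analysed.** This stands. Tables 98 and 99 give in-window n and % by arm and age stratum, and SAP 9.3.2 names Table 99 as the display for the related non-serious endpoint. A reader might infer that an endpoint analysis is missing; the documents do not support that. What is missing is the interval and the severity and relatedness splits within the window.

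**Twelve months is an inference.** No sentence says that Tables 94-96 run to 12 months. SAP 4.5.1 lists non-serious unsolicited AEs (to 21 days) apart from MAAEs and PIMMCs (to 12 months), and the all-AEs sentence could mean regardless of severity or relationship. This is a possible reading, but it sits badly with the unqualified inclusion rule, the serious-or-non-serious wording and the explicit windows given only to Tables 98-100. The window needs to be stated.

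**Table 97 is different.** It holds only related non-serious AEs, so background visits judged unrelated cannot enter it, nor the related columns of Table 96. This stands. Table 97 shares the missing window but not the full mixture.

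**The dilution may be small.** Subjects are in good health, the trial is descriptive, and Table 98 still shows the undiluted contrast. A reader might infer a large distortion from the long follow-up, but the documents give no rates to support one.

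**MAAEs by listing is the protocol's choice.** This stands. Listing 11 flags them and Table 73 gives a count by arm. The absence of an MAAE table with CIs does not breach the plan.

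**Early release.** Tables 94-96 are marked for the Preliminary Report, whose cut is Day 202 in SAP 6.2.2 and Day 43 in SAP 6.6. A reader might see a conflict between calling that release final and later showing different numbers in the CSR. SAP 6.2.2 calls it final for the data it contains, so a CSR table with longer follow-up is an update, not a contradiction.

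**Conclusion.** The point holds as a gap in specification and display. On the plain reading of SAP 9.3.2, Tables 94-96 and Figures 21-24 in the CSR combine complete AE collection through 21 days after each dose with SAE/MAAE/NOCMC/PIMMC-only collection to about 12 months. The only unsolicited-AE intervals therefore do not describe the 21-day endpoints, although Protocol 11.6.2 plans exact intervals for AEs.

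The direction of the effect is clear if late events do not depend on arm: higher percentages and smaller absolute differences. Its size cannot be known from the documents. The illustrated loss of 0.5 to 3 points from a 10-point difference rests entirely on assumed rates and on independence. No hypothesis test or trial decision depends on these tables, so this is an inexpensive improvement and not a threat to the safety conclusions.

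**What to change.** Replace the all-AEs sentence in SAP 9.3.2 with a stated onset window, from each vaccination through 21 days after it, for Tables 94-97 and Figures 21-24. Put the window in the titles or footnotes, as Tables 98-99 already do. At minimum, add exact 95% CIs to the Day 1-22 Post Any Vaccination columns of Tables 98-99 and footnote the period that Tables 94-97 cover.

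Show later SAE/MAAE-type events separately so that they are not lost. One option is a display of subjects with any MAAE from the first dose through 12 months, by arm and age stratum, with exact 95% CIs.

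The cost is SAP wording, a date filter on data already held and one extra display. Percentages in Tables 94-97 will be no higher than under the present rule, and lower wherever late events would have counted. Late events will appear in their own display and in the existing listings.

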9.4. Deaths, Serious Adverse Events and other Significant Adverse Events

The following listings will be presented including Subject ID, Age (years) AE Description, AE Onset Date/End Date, Last Vaccination Received/Days Post Vaccination, Reason Reported as an SAE, Relationship to Treatment, Alternate Etiology if not Related, Outcome, and Duration of Event (days):

- Deaths and Serious Adverse Events (Table 101);
- Adverse Events of Special Interest (Table 102);
- New Onset Chronic Medical Conditions (Table 103).

A listing of all reported AEs by subject will be presented in Listing 11, sorted by Treatment Arm, Age Stratum, Subject ID, and AE Number.

9.5. Pregnancies

For any subjects in the Safety population who became pregnant during the study, every attempt will be made to follow these subjects to completion of pregnancy to document the outcome, including information regarding any complications with pregnancy and/or delivery. Listing 17, Listing 18, Listing 19, Listing 20, and Listing 21 will present any study pregnancies and their outcomes.

9.6. Clinical Laboratory Evaluations

Clinical safety laboratory parameters (WBC, Hgb, PLT, ALT, T. Bili, Cr) will be collected from each subject prior to each study vaccination and approximately 7 days after each study vaccination. These evaluations will be performed by the central clinical laboratory. The grading scale for clinical laboratory evaluations is presented in Table 13. Clinical laboratory evaluations assessed on Day 1 prior to the first study vaccination will be considered as baseline.

The distribution of laboratory results by severity, study day, treatment arm and age stratum will be presented in Table 105, Table 106, Table 107, Table 108, Table 109, Table 110, and Table 111. Descriptive statistics including mean, standard deviation, median, minimum and maximum values by study day will be summarized for each parameter in Table 112, Table 113, Table 114, Table 115, Table 116, and Table 117, and for the change from baseline for each parameter in Table 118, Table 119, Table 120, Table 121, Table 122, and Table 123. Box plots illustrating the change from baseline for each laboratory parameter will be presented in Figure 25, Figure 26, Figure 27, Figure 28, Figure 29, and Figure 30. Subject

visits with abnormal laboratory results, Grade 1 severity or higher, will be presented in Table 124 and Table 125 for Chemistry and Hematology parameters, respectively.

A complete listing of individual clinical laboratory results will be presented in Listing 12 and Listing 13 for chemistry and hematology, respectively, sorted by subject ID, parameter, and visit number.

9.7. Vital Signs and Physical Evaluations

Vital signs oral temperature, systolic blood pressure, diastolic blood pressure, and pulse will be assessed prior to study vaccination on Day 1 and Day 22. The grading scale for vital sign evaluations is presented in Table 12. Summaries of vital signs by maximum severity will be tabulated by visit, treatment arm, and age stratum (Table 126, Table 127, Table 128, Table 129, and Table 130). A listing of vital signs will be presented (Listing 14).

Targeted physical examinations will be performed, if indicated, based on a subject's medical history. A listing of physical exam findings will be presented (Listing 15).

9.8. Concomitant Medications

Concomitant medications will be collected for the 30 days prior to the first study vaccination through 21 days after the second study vaccination. Concomitant medications will be coded to the Anatomical Therapeutic Classification using the WHO Drug Dictionary. The use of prior and concomitant medications taken during the study will be recorded on the CRFs. A by-subject listing of concomitant medication use will be presented (Listing 16). The use of concomitant medications during the study will be summarized by ATC1, ATC2 code, treatment arm and age stratum for the Safety population (Table 131 and Table 132).

